7.4. Data Sources

The information that will be used in the study comes exclusively from secondary sources. Two databases will be used to extract the information:

7.4.1. Claim Database

Claim databasee contains all prescriptions of all patients' medications chronologically. From this database, the index date will be established and the diagnosis of NVAF of the patient will be extracted. Similarly, this base will be used to assess the persistence on therapy and treatment patterns (duration of treatment, changes, persistence), pharmacy claim information, demographic information, diagnosis and insurance data.

7.4.2. Medical Record

Of the patients identified from the claim database, information will be extracted from the second database, the medical record, it will serve to characterize patients based on their baseline demographic and clinical characteristics, that is, on the index date. In turn, it contains the main control variables and the information related to the outcomes of interest, stroke and bleeding events.

7.5. Study Size

The total population of patients treated with OAC between January 1, 2013 and June 30, 2018 was analyzed in the claim dabtabase. For the purpose of the study, it contains the information of 7,500 patients, once they were verified that they met the inclusion criteria of the study. This means that patients who start warfarin and NOACs would be included within this period. Patients who initiate NOACs within the established period and who have been exposed to warfarin before 2013 will also be included.

7.6. Data Management

The data sources are databases owned by the investigator, he will execute the data management for this study.

7.6.1 Electronic Case Report (ECR)

As used in this protocol, the term ECR should be understood to refer to either a paper form or an electronic data record or both, depending on the data collection method used in this study. ECR is required and should be completed for each included patient. The completed original ECRs are the sole property of Pfizer and should not be made available in any form to third parties, except for authorized representatives of Pfizer or appropriate regulatory authorities, without written permission from Pfizer. The party performing medical record review shall ensure that the ECRs are securely stored at the study site in encrypted electronic form and will be password protected to prevent access by unauthorized third parties.

PFIZER CONFIDENTIAL

The party performing medical records review has ultimate responsibility for the abstraction of all clinical, safety, and laboratory data entered on the ECRs and any other data collection forms (source documents).

In order to ensure the accurate, complete, consistent, timely enduring of the data, Pfizer and the third party will design and validate the ECR from review of 30 medical records to guarantee the operationalization adequate of the variables, identifying alternative coding data available (abbreviations, synonyms, symbols, units, etc) and setting of the variables following this protocol. From the results of the validation and the standard operating procedures of Pfizer, data management plan, data review plan, ECR completion instruction and data entry guidelines will be built to ensure the consistency and accurate of data. and distributed to different physicians who participate in the abstraction of the data.

The personal responsible to abstract the data will be physicians who will be trained in the abstraction process, use of manuals and ECR. These group will be blinded of the objective of the study in order to avoid the reviewer bias. The party will responsible to conduct and record this activity.

Likewise, the party execute monitoring of the data which will be follow the guidelines described in the data review plan and data quality control plan as required by the Pfizer policy. Finally, the concordance of the abstracters, the intrarater and interrater reliability, will be measured for cohens kappa and interclass correlation, respectively.

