7.3. Variables

The described variables are classified into two variable groups according to the role, the clinical outcome and baseline (demographic, clinical, treatment variables). The latter include the possible subgroups to consider. These analyses are initially exploratory to the extent that the specific analyses may be performed according to the sample collected.

Table 1. Table of Variables

Variable	Role	Data source (s)	Operational definition
Age	Demographic characteristic	Medical record	Birthday
Gender	Demographic characteristic	Medical record	Male, female, other
Race	Demographic characteristic	Medical record	White, half-breed, indigenous, black, others
Weight	Demographic characteristic	Medical record	Kg
Height	Demographic characteristic	Medical record	Mt (meters)
Body mass index	Demographic characteristic	Medical record	Kg/mt ²
City of residence	Demographic characteristic	Medical record	Cities of Colombia
Time to diagnosis to NVAF	Clinical characteristic	Medical record	Date (dd/mm/yy)
High alcohol intake at OAC prescription date	Clinical characteristic	Medical record	Yes, No

Variable	Role	Data source (s)	Operational definition
Diabetes	Clinical characteristic	Medical record	No, without chronic complication, with end-organ damage
Liver disease	Clinical characteristic	Medical record	No, mild, moderate, severe
Hypertension	Clinical characteristic	Medical record	Diagnosis of hypertension (Yes, No)
Uncontrolled hypertension at OAC prescription date	Clinical characteristic	Medical record	Yes, No
Rheumatic disease	Clinical characteristic	Medical record	Yes, No
Acquired Immune Deficiency Syndrome (AIDS)	Clinical characteristic	Medical record	Yes, No
Severe renal disease (dialysis, organ transplant)	Clinical characteristic	Medical record	Yes, No
Moderate renal disease (creatinine > 3 mg/dL)	Clinical characteristic	Medical record	Yes, No
Chronic heart failure	Clinical characteristic	Medical record	Yes, No
Myocardial infarction	Clinical characteristic	Medical record	Yes, No
Chronic obstructive pulmonary disease (COPD)	Clinical characteristic	Medical record	Yes, No
Peripheral vascular disease	Clinical characteristic	Medical record	Yes, No
Stroke or transient ischemic attack (TIA)	Clinical characteristic	Medical record	Yes, No
Dementia	Clinical characteristic	Medical record	Yes, No
Hemiplegia	Clinical characteristic	Medical record	Yes, No
Connective tissue disease	Clinical characteristic	Medical record	Yes, No

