Leukemia	Clinical characteristic	Medical record	Yes, No

PFIZER CONFIDENTIAL

Variable	Role	Data source (s)	Operational definition
Malignant lymphoma	Clinical characteristic	Medical record	Yes, No
Peptic ulcer disease	Clinical characteristic	Medical record	Yes, No
Metastatic solid tumor	Clinical characteristic	Medical record	Yes, No
History of ischemic or hemorrhagic stroke	Clinical characteristic	Medical record	Yes, No
History of TIA	Clinical characteristic	Medical record	Yes, No
History of de tromboembolismo	Clinical characteristic	Medical record	Yes, No
Enfermedad coronaria	Clinical characteristic	Medical record	Yes, No
History of de hemorragia gastrointestinal	Clinical characteristic	Medical record	Yes, No
History of Intracranial bleeding	Clinical characteristic	Medical record	Yes, No
History of Other bleeding	Clinical characteristic	Medical record	Yes, No
Bleeding history or predisposition at start OAC treatment	Clinical characteristic	Medical record	Yes, No
INR > 60% at start OAC treatment	Clinical characteristic	Medical record	Yes, No
Use of aspirin at start OAC treatment	Clinical characteristic	Medical record	Yes, No
Use of clopidogrel at start OAC treatment	Clinical characteristic	Medical record	Yes, No
Use of NSAIDs at start OAC treatment	Clinical characteristic	Medical record	Yes, No
HASBLED at start OAC treatment	Clinical characteristic	Medical record	Score – number higher than 0
CHA2DS2-VASc at start OAC treatment	Clinical characteristic	Medical record	Score – number higher than 0
Anaemia at start OAC treatment	Clinical characteristic	Medical record	Yes, No
Stroke	Clinical outcome	Medical record	Yes, No
Time to stroke	Clinical outcome	Medical record	Date of event dd/mm/yy

Pfizer Confidential

Variable	Role	Data source (s)	Operational definition
Type of stroke	Clinical outcome	Medical record	Ischemic stroke, Haemorrhagic or not specified
Pulmonary embolism	Clinical outcome	Medical record	Yes, No
Time to pulmonary embolism	Clinical outcome	Medical record	Date of event dd/mm/yy
Gastrointestinal bleeding	Clinical outcome	Medical record	Yes, No
Time to gastrointestinal bleeding	Clinical outcome	Medical record	Date of event dd/mm/yy
Intracranial bleeding	Clinical outcome	Medical record	Yes, No
Time to Intracranial bleeding	Clinical outcome	Medical record	Date of event dd/mm/yy
Other major bleeding	Clinical outcome	Medical record	Yes, No
Time to other major bleeding	Clinical outcome	Medical record	Date of event dd/mm/yy
CCI			

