Persistence	Clinical outcome	Claim databases	Yes, No
OAC treatment	Treatment	Claim databases	Warfarin, apixaban, rivaroxaban, dabigatran
Diagnosis at index date	Treatment	Claim databases	Diagnosis AF based on ICD-10
Date of OAC prescription	Treatment	Claim databases	Date reported dd/mm/yy
Dosage of the initial OAC treatment	Treatment	Claim databases	Mg per dose
Initial frequency of OAC treatment	Treatment	Claim databases	Number of doses at initial OAC treatment
OAC escalation	Treatment	Claim databases	Yes, No
Type of OAC escalation	Treatment	Claim databases	Dose increase or dose decrease
Time to OAC escalation	Treatment	Claim databases	Date reported dd/mm/yy
CCI			

Variable	Role	Data source (s)	Operational definition
CCI			
INR testing monthly in patients with warfarin	Treatment	Medical record	INR reported in the medical record per month
Switch to another OAC treatment:	Treatment	Claim databases	Yes, No
Time to Switch to another OAC treatment	Treatment	Claim databases	Date reported dd/mm/yy
Causa de cambio	Treatment	Medical record	Adverse events, effectiveness, adherence, patient preference, administrative problems, not reported, others
Concomitant therapies by OAC prescription	Treatment	Medical record	NSAIDs, Angiotensin-converting-enzyme (ACE) inhibitors, Amiodarone, Beta-blockers, Angiotensin II receptor blockers (ARBs), Aspirin, Clopidogrel, Digoxin, Diuretics, calcium blockers, statins, proton pump inhibitor, selective H2 antagonists, antidiabetics, insulin, serotonin reuptake inhibitors
Previously exposed to warfarin	Treatment	Claim databases	Yes, No

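### Section 7.6.1 chooses the abstractor-agreement statistic by rater comparison instead of by variable type, which is wrong for about a third of the chart-abstracted variables

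*Combined protocol and SAP*

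**What the plan says.** Section 7.6.1 describes chart abstraction by trained physicians. The guidelines are to be "distributed to different physicians who participate in the abstraction of the data", so agreement between abstractors matters as well as each abstractor's consistency. The section ends by stating that "the intrarater and interrater reliability, will be measured for cohens kappa and interclass correlation, respectively". The last word pairs kappa with the intrarater comparison and the correlation with the interrater comparison. Variable type is not mentioned.

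Nothing else in the document changes this. Section 7.6.4 (collection of information) and Section 7.8 (quality control) name no agreement statistic, and Annex 1 lists no stand-alone documents. Section 7.6.1 mentions a data review plan and a quality control plan, but no agreement statistic from either is given. The number of charts to be abstracted twice and an acceptable level of agreement are not stated.

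Table 1 (Section 7.3) shows that the medical-record variables are of several kinds:

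- Yes/No items, including stroke, pulmonary embolism and each type of bleeding.
- Unordered categories, such as race ("White, half-breed, indigenous, black, others") and type of stroke ("Ischemic stroke, Haemorrhagic or not specified").
- Dates, including five outcome times recorded as "Date of event dd/mm/yy".
- Scores ("Score – number higher than 0").
- Measurements, such as weight, height and "INR reported in the medical record per month".

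**The concern.** The right agreement statistic depends on the measurement scale of the variable, not on whether one or two people did the reading. Kappa compares exact matches with those expected by chance, so it suits categories. Without weights it treats a difference of 1 kg the same as one of 40 kg. The ICC compares variation between patients with total variation, so it suits quantities. On unordered categories it treats arbitrary code numbers as if they were measurements.

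As written, nominal items would get an unsuitable statistic between raters, and numeric and date items an unsuitable one within raters. At stake is whether the planned reliability results can be interpreted. Section 7.9 accepts that outcome diagnoses may be misclassified, and this is the only quantitative agreement measure the plan names.

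**Working it through.** The plan states no reliability figure, so there is none to reproduce. The check has two parts: how many variables are affected, and how the two statistics behave on each kind of variable.

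**Count.** These are the Table 1 rows whose source is the medical record.

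| Kind | Number | Contents |
|---|---|---|
| Yes/No | 37 | comorbidities, history, baseline drug use, stroke, pulmonary embolism, bleeding |
| More than two categories | 8 | gender, race, city, diabetes, liver disease, type of stroke, cause of switch, concomitant therapies |
| Numeric, score or date | 13 | birth date/age, weight, height, BMI, NVAF diagnosis date, HAS-BLED, CHA2DS2-VASc, five event dates, monthly INR |

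Total: 37 + 8 + 13 = 58. At least one assigned statistic is unsuitable for 8 + 13 = 21 (36%). Diabetes and liver disease have ordered categories, for which an ICC on ranks can be defended, so the lower count is 19 (33%). Some rows are redacted, and concomitant therapies could be scored as separate Yes/No items, so the tally is approximate.

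**Formulas.** Kappa = (po − pe)/(1 − pe), where po is observed and pe chance agreement. For two readings with variances v1 and v2, covariance c and mean difference d, the two-way agreement ICC in large samples is 2c/(v1 + v2 + d²).

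**Yes/No items.** Let the two readings be positive with probabilities p1 and p2, and both positive with probability p11.

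- po − pe = 2(p11 − p1·p2) = 2c.
- 1 − pe = p1 + p2 − 2·p1·p2 = v1 + v2 + d².

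The two statistics are therefore identical in large samples. In simulation (prevalence 5% or 30%, 5% misclassification per reading) the largest difference was 0.0085 with 30 charts and below 0.001 with 300.

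**Unordered categories.** Assume three categories A, B and C with shares 0.6, 0.2 and 0.2, where the second reader records 20% of the As as C. The second reader's shares are then 0.48, 0.20 and 0.32.

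- po = 0.48 + 0.20 + 0.20 = 0.88.
- pe = 0.6×0.48 + 0.2×0.2 + 0.2×0.32 = 0.392.
- Kappa = 0.488/0.608 = 0.80, however the categories are numbered.
- ICC with A, B, C = 0, 1, 2: 2×0.496/(0.640 + 0.7744 + 0.24²) = 0.67.
- ICC with A, B, C = 1, 0, 2: 2×0.400/(0.400 + 0.5056 + 0.12²) = 0.87.
- ICC with A, B, C = 0, 2, 1: 2×0.568/(0.640 + 0.6016 + 0.12²) = 0.90.

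The same readings give three different ICCs. A simulated set of 300 charts gave kappa 0.82 and ICCs of 0.69, 0.89 and 0.92.

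**Numeric items and dates.** The result depends on the assumed error.

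- *Weight, independent error of SD 1 kg in each reading, true SD 14 kg:* ICC = 196/197 = 0.99. Simulated kappa averages 0.26 on whole kilograms and 0.03 if recorded to 0.1 kg.
- *Weight, copying slips in 5% of records (±1 or ±10 kg):* po is about 0.95 and pe about 1/(2√π × 14) = 0.02, so kappa is about 0.93/0.98 = 0.95. The mean squared slip is 0.05 × (1 + 100)/2 = 2.5, so the ICC is about 392/394.5 = 0.99. With slips in 2% or 10% of records, simulated kappa is 0.98 or 0.90.
- *Dates over 1,500 days, each reading off by up to 3 days:* simulated kappa 0.17, ICC above 0.999.

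**The case against.** The sentence may be a drafting slip. Its English is loose, and kappa for categories with ICC for quantities may be what was meant. That is plausible, but anyone following the text would do something else, so it still needs correcting.

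A reader might go further than the documents allow in four ways.

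- *That stroke and bleeding would have no usable interrater measure.* No kappa would be reported between raters, but an ICC on 0/1 data is nearly the same number. The Yes/No outcomes would still get a valid coefficient.
- *That every outcome is categorical and so gets the wrong interrater statistic.* Table 1 lists five outcome times as dates, for which an interrater ICC is suitable.
- *That near-perfect agreement on measurements would be reported as poor.* This follows only if each reading carries fresh error, as if the patient were weighed again. Sections 7.6.1 and 7.6.4 describe copying recorded values. With occasional slips, kappa stays at 0.90 to 0.98.
- *That rater agreement is the plan's main evidence on misclassification.* Section 7.9 relies on outcome definitions and the case report format. The plan also has a 30-record form validation, a 20-chart pilot, trained abstractors blinded to the objective, and checks against source documents.

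All four of these limits stand. None of them rescues the interrater ICC on unordered categories, or makes unweighted kappa a sound general choice for quantities and dates.

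**Conclusion.** The rule in Section 7.6.1 is wrong as written, with low severity. It affects about 19 to 21 of 58 chart-abstracted variables, roughly a third. The clearest failure is the interrater ICC on unordered categories (race, city, type of stroke, cause of switch), where the result depends on arbitrary numbering: 0.67 to 0.90 against a kappa of 0.80 in the worked example. For numeric items, scores and dates, an unweighted intrarater kappa discards the size of the disagreement. Whether that matters much or little depends on the error pattern, which the documents do not give. For the 37 Yes/No items the choice is unconventional but not materially wrong.

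The error rates, prevalences and chart numbers used here are assumptions. The dependence on category numbering and the near-equality for Yes/No items do not rest on particular values of them. The problem is confined to a data-quality check and changes none of the study's main estimates.

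**What to change.** Replace the sentence in Section 7.6.1 with a rule by variable type. For both intrarater and interrater agreement, use Cohen's kappa for categorical variables (weighted where the categories are ordered, as for liver disease and diabetes). Use the intraclass correlation, with its model stated, for continuous variables, scores and dates. Correct the term to intraclass: an ordinary correlation would miss a constant shift between readers (a 10 kg shift gives a correlation of 1.00 against an ICC of 0.80 in simulation). Report interrater agreement separately for stroke, embolism and bleeding.

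It would also help to state how many charts are abstracted twice. For dates, a summary of differences in days would be useful, because dates spread over years push the ICC close to 1 even when errors matter.

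The cost is one or two sentences. The same duplicate abstractions serve, and no further data are needed.

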7.6.2 Record Retention

To enable evaluations or inspections/audits from regulatory authorities or Pfizer, third party responsible for performing medical record review agrees to keep all study-related records, including the identity of all participating patients (sufficient information to link records, e.g., ECRs and medical records), ECR file, safety reporting forms, source documents, detailed records of treatment disposition, and adequate documentation of relevant correspondence (e.g., letters, meeting minutes, and telephone call reports). The records should be retained by third party responsible for performing medical record review according to local regulations or as specified in the vendor contract, whichever is longer. Third party responsible for performing medical record review must ensure that the records continue to be stored securely for so long as they are retained.

If third party responsible for performing medical record review becomes unable for any reason to continue to retain study records for the required period, Pfizer should be prospectively notified. The study records must be transferred to a designee acceptable to Pfizer.

Study records must be kept for a minimum of 15 years after completion or discontinuation of the study, unless third party responsible for performing medical record review and Pfizer have expressly agreed to a different period of retention via a separate written agreement. Record must be retained for longer than 15 years if required by applicable local regulations.

The third party responsible for performing medical record review obtain Pfizer's written permission before disposing of any records, even if retention requirements have been met.

7.6.3 Patient Identification

The Investigators will identify patients from the claim database, initially, in this database the type of therapy with any of the OACs will be verified, and then that they meet the inclusion criteria of the study.

7.6.4 Collection of Information

For the analysis of the data, the statistical package Statistical Package for the Social Sciences (SPSS) Statistics, version 26.0 (IBM, US) for Windows will be used.

Data collection will be performed by healthcare providers following a data collection template developed in Microsoft Excel. For the purpose of unifying criteria and concepts, the template will be parametrized according to the possible responses or options for each variable, which will be defined by the medical expertise, information availability and published clinical studies. The template will be then validated according to a pilot testing of 20 randomly selected clinical charts.

Data collection will be performed after verifying the inclusion and exclusion criteria by the investigation staff. Firstly, the data regarding demographic data and delivery of the medications of interest to the patients meeting the criteria will be reviewed and collected. Subsequently, the electronic medical chart will be reviewed for collecting the clinical data will be identified.

In order to ensure protection of the patient's personal data and maintain high confidentiality and protection of the personal data according to the corporative policy 404 on *Protecting the Privacy of Personal Data*, the vendor will not transfer the collected database.

Pfizer will monitor the vendor to ensure the protection of the patient's personal data.

7.6.5 Database Retention

The Principal Investigator will store the database, adverse event reports and relevant correspondence securely to prevent unauthorized personnel from accessing the information.

7.7 Data Analysis

This type of analysis is descriptive and explanatory, as it depends largely on the sample size. Continuous variables will be presented as means, standard deviation or other measures of central tendency or position, while categorical variables will be presented as frequencies and percentages.

Regarding bivariate analyses of continuous variables with normal behavior, the Student's t test will be performed. In case of presenting non-normal behavior, the Mann-Withney test will be used. For variables that are continuous with several categories, analysis of variance (ANOVA) will be assessed. In the event of presenting a non-normal behavior, the multivariate analysis of

variance (MANOVA) test will be carried out. For categorical variables, the X² test will be used.

Exploratory analyses based on sample size:

The cumulative incidence of clinical outcomes (Stroke/ systemic embolism and major bleeding) will be calculated throughout the study period, from which the incidence or survival curves will be derived using the Kaplan Meier method. Incidence of events will be explored in clinically relevant subgroups based on sample size.

For the execution of the analysis, CCI and change of treatment, and missing treatments are considered as censures. Treatment comparison will be not conducted.

A similar analysis will be performed for the group of patients who have not presented stroke/ systemic embolism or major bleeding events to estimate the time for CCI change of treatment.

In the independent variables, the significance will be analyzed, as a level of statistical significance p < 0.05.

